Protocol Amendment 7: 25 April 2016

Applicable to all countries and study centers.

At the time of this amendment, 35 subjects had been randomized in the study.

** OPV116910 Amendment 6 was not implemented at any study center. As a result, conduct of the study for all study centers transitioned from Amendment 5 directly to Amendment 7 (ie, nonconsecutive numbering) **

Section	Original Text	Changes	Rationale
Title page	NA	Protocol amendment number, date, and revision chronology.	Amendment 7
Protocol-specific definitions; Protocol summary, Study design; Section 3.1	If B-cell counts have not recovered by the Week 60 visit, subjects not entering the extension study will remain in an Individualized Follow-up Period until either the CD19+ B-cell counts or circulating IgG levels are \geq LLN or baseline levels (if $<$ LLN) or until 2 years after the last dose of investigational product (whichever comes first).	If B-cell counts have not recovered by the Week 60 visit, subjects not entering the extension study will remain in an Individualized Follow-up Period until both the CD19+ B-cell counts and circulating IgG levels are \geq LLN or baseline levels (if $<$ LLN) or until 2 years after the last dose of investigational product (whichever comes first).	Based on discussion with investigators, criteria for maintaining subjects in the Individualized Follow-up Period were modified to allow for improved safety monitoring following last dose of investigational product, while facilitating the exit of subjects from the study in order to progress to alternative treatment if needed.
Section 3.1, Figure 3-2	Meet any of these criteria: 
 • CD19+ B-cells or IgG \geqLLN or baseline? • Meet other criteria for study withdrawal/exit? • 2 years after the last dose? AND HBV monitoring complete (if applicable)?	Meet any of these criteria: 
 • CD19+ B-cells and IgG \geqLLN or baseline? • Meet other criteria for study withdrawal/exit? • 2 years after the last dose? AND HBV monitoring complete (if applicable)?	
Section 3.1.3	If B-cell counts have not recovered by the Week 60 visit, subjects not entering the extension study (OPV117059) will remain in Individualized Follow-up until: 
 • CD19+ B-cell counts or circulating IgG levels are \geqLLN or baseline levels (if $<$LLN) 	If B-cell counts have not recovered by the Week 60 visit, subjects not entering the extension study (OPV117059) will remain in Individualized Follow-up until: 
 • CD19+ B-cell counts and circulating IgG levels are \geqLLN or baseline levels (if $<$LLN) 	

Section	Original Text	Changes	Rationale
Section 6, Table 6-2	a. Subjects entering the individualized follow-up period continue to be monitored every 12 weeks, until CD19+ B-lymphocyte counts or IgG recover to LLN or to the subject's Baseline value (if <LLN) or if criteria for study withdrawal are met or for a maximum of 2 years after the last dose of ofatumumab SC.	a. Subjects entering the Individualized Follow-up Period continue to be monitored every 12 weeks, until CD19+ B-lymphocyte counts and IgG recover to \geq LLN or to the subject's Baseline value (if <LLN) or if criteria for study withdrawal are met or for a maximum of 2 years after the last dose of ofatumumab SC.	Based on discussion with investigators, criteria for maintaining subjects in the Individualized Follow-up Period were modified to allow for improved safety monitoring following last dose of investigational product, while facilitating the exit of subjects from the study in order to progress to alternative treatment if needed.
Section 5.3	Sponsor unblinding for analyses will occur after all subjects have completed the Week 60 visit or been withdrawn from the treatment period (see Section 8.3.4).	Sponsor unblinding for analyses will occur after all subjects have completed the Week 60 visit, been withdrawn from the treatment period, or the study has been terminated.	Given the study had been terminated, the Sponsor unblinded subjects' randomized treatment assignments to provide information for the investigators' continued monitoring of their subjects.

Protocol Amendment 8: 05 Sep 2016

Applicable to all countries and study centers.

At the time of this amendment, 35 subjects had been randomized in the study.

Section	Original Text	Changes	Rationale
General	NA	
From Section 1 through Section 9.9, did not abbreviate a term if it is used only once.
 
Defined an abbreviation at the point of first use in the text.
 
Defined abbreviations used in a table in a table footnote.
	
Treated Section 1 through Section 9.9 as the main body of the document when verifying abbreviation usage.

Title page	NA	
Protocol amendment number, date, and revision chronology.
	
Amendment 8

Throughout	NA	
All mentions of GlaxoSmithKline / GSK changed to Novartis. Legal registered and contact addresses updated.
	
Transition of protocol Sponsor

Title page; Sponsor information page; Protocol summary	NA	
Novartis Study IDs added as follows: Core Study: OPV116910 (also known as COMB157J2301)
	
Transition of protocol Sponsor; Novartis study ID format required for Novartis administrative purposes. Novartis study IDs added at first usage in both protocol summary and main text; GSK ID only used at subsequent instances.

Study design; Section 3.1; Section 3.1.3	NA	
Novartis Study IDs added as follows: Extension Study: OPV117059 (also known as COMB157J2301E1)
	
Transition of protocol Sponsor; Novartis study ID format required for Novartis administrative purposes. Novartis study IDs added at first usage in both protocol summary and main text; GSK ID only used at subsequent instances.

Section	Original Text	Changes	Rationale								
Protocol-specific definitions; Protocol summary, Study design; Section 3.1; Figure 3-2, Section 3.1.3, Section 6, Table 6-2; Section 5.3	NA	Protocol Amendment 7 was incorporated in the full protocol document as part of the Amendment 8 updates because previously only a summary of changes version was available.									
Protocol Summary, Study Design; Section 3.1; Section 5.7	Subjects completing the study and meeting entry criteria will be offered the option to participate in an extension study (OPV117059), which will start after completion of the Week 60 visit.	As the ofatumumab development program in the indication PV has been terminated , subjects completing the study will no longer be eligible to participate in the extension study (OPV117059). Subjects who were enrolled in the extension study prior to program termination may remain in the extension study until exit criteria are met.	Text was updated based on the ofatumumab development program in the indication PV having been terminated.								
Section 6.3.6	To ensure subject safety, each pregnancy must be reported to GSK within 2 weeks of learning of its occurrence.	To ensure subject safety, each pregnancy must be reported to Novartis within 24 hours of learning of its occurrence.	Transition of protocol Sponsor								
Section 6.3.9, Table 6-4	
  
 Type of Event	Time Frame	
   
 Pregnancy	2 weeks	
  
	Type of Event	Time Frame	Pregnancy	2 weeks	
  
 Type of Event	Time Frame	
   
 Pregnancy	24 hours	
  
	Type of Event	Time Frame	Pregnancy	24 hours	
Type of Event	Time Frame										
Pregnancy	2 weeks										
Type of Event	Time Frame										
Pregnancy	24 hours										
Section 7	Adverse events and concomitant medications terms will be coded using MedDRA and an internal validated medication dictionary, GSKDrug .	Adverse events and concomitant medications terms will be coded using the Medical Dictionary for Regulatory Activities (MedDRA) , the World Health Organization Drug Dictionary , and an internal validated medication dictionary.	Updated to provide expanded MedDRA term at first use and to include the World Health Organization Drug Dictionary and to remove the GSKDrug specification.								
Section 10	NA	Ofatumumab/OMB157/GSK18411 57 Investigator's Brochure (IB). Version 09. Document number 090095a888b3fd50. 12 April 2016	Reference for ofatumumab Investigator's Brochure added to protocol body references in Section 10. Cross-references to the Investigator's Brochure hyperlinked in protocol body to the citation in the list of references in Section 10.								

Section	Original Text	Changes	Rationale
Throughout	Investigator's Brochure	Investigator's Brochure [Ofatumumab/OMB157/GSK184 1157 Investigator's Brochure, 2016]	Further detail and year added to Investigator Brochure references for clarity and consistency with format of other references.

Division: World Wide Development

Retention Category: GRS019

Information Type: Reporting and Analysis Plan

Title: Reporting and Analysis Plan for OPV116910: A Randomized, Double-Blind, Placebo-Controlled, Parallel-Group Study to Investigate the Efficacy and Safety of Ofatumumab Injection for Subcutaneous Use in Subjects with Pemphigus Vulgaris

Compound Number: GSK1841157 / NCT01920477

Effective Date: [29-MAR-2018] Based on Protocol dated 28-SEP-2015 amendment 6

Description: Ofatumumab is a novel human IgG1k lytic monoclonal antibody (mAb) that specifically binds to the human CD20 antigen, which is expressed only in B lymphocytes from the pre-B-cell stage to the plasmacytoid immunoblast stage.

This global study will investigate the efficacy, safety, and tolerability of ofatumumab injection for subcutaneous (SC) use in the treatment of subjects with pemphigus vulgaris. The primary objective of the study is to determine the efficacy, based on disease remission, of ofatumumab SC at a dose of 20 mg administered every 4 weeks (with an additional 20 mg ‘loading’ dose [ie, 40 mg total] at both Week 0 and Week 4) in subjects with pemphigus vulgaris. Other objectives include evaluation of safety, tolerability, B-cell depletion and repletion, anti-desmoglein antibody levels, immunogenicity, pharmacokinetics, and other clinical and quality of life endpoints.

Subject: pemphigus vulgaris, ofatumumab, monoclonal antibody

Author’s Name, Title and Functional Area:

[Redacted]

Approved by:

[Redacted]

Date

[Redacted]

Date

For business use only
 May not be used, divulged, published or otherwise disclosed
 without the consent of Novartis

Modification History

Date	Version	Details
07-Apr-2017	Final Draft	Final Draft version
29-Mar-2018	Amendment	
Updated to detail about PK/PD/PGx analysis
 
 • PK data: Only PK Plasma trough concentration data will be summarized and listed on PK population. • PD data: The PD Biomarker data (B-Cell panel and Neutrophil counts data only) will be summarized by Sex and time point. Other PD endpoints analysis as mentioned in section 2.2.6 Pharmacodynamic endpoints ('Time to repletion of CD19+ B-cell...' and 'B-cell depletion and repletion...') will not be performed. • PGx data: Pharmacogenetics results data not available and beyond the scope of this RAP. Hence no Pharmacogenetics analysis can be performed. 'Section 15 Pharmacogenetic data analyses' removed.

TABLE OF CONTENTS

[figure not shown]

DNA	deoxyribonucleic acid
Dsg	desmoglein
ECG	echocardiography
eCRF	electronic case report form
HAHA	human anti-human antibody
hsCRP	high sensitivity C-reactive protein
IDMC	independent data monitoring committee
IP	investigational product
ITT	Intent-to-Treat (population)
IV	intravenous
IVR	interactive voice response
kg	kilogram
kg/m ²	kilograms per meter-squared
LLN	lower limit of normal (reference range)
MAB	monoclonal antibody
MedDRA	Medical Dictionary for Regulatory Activities
mg	milligram
min	minute
mL	milliliter
PCR	polymerase chain reaction
PD	pharmacodynamic
[REDACTED]	[REDACTED]
PGx	pharmacogenetics
PK	pharmacokinetic
PML	progressive multifocal leukoencephalopathy
PP	Per Protocol (population)
PT	preferred term

PV	pemphigus vulgaris
RBC	red blood cells
RRMS	relapsing-remitting multiple sclerosis
SAE	serious adverse event
SC	subcutaneous
SI	International System of Units
SOC	system organ class
SR	sustained remission
TLF	tables, listings and figures
	
UK	United Kingdom
US	United States
WBC	white blood cells

1. INTRODUCTION

At the time of SAP finalization, the sponsorship of the study was transferred from GSK to Novartis. All the core analyses were kept as per the original protocol analysis plan. However, because the study was terminated early with a limited sample size (total of 69 patients), the analyses plan was reduced or simplified. Due to the low sample size all subgroup analyses were removed and the multiplicity procedure omitted. All statistical tests will be performed at the two-sided 5% level.

Because advanced versions of the SAP and table/listing/figure documents already existed, the format of these documents were not changed to Novartis templates. All Table/listings/ figures will follow Novartis conventions for outputs for a Novartis clinical study report.

1.1. Disease Background

Pemphigus vulgaris (PV) is an acquired, rare, chronic, debilitating, and potentially life-threatening autoimmune vesiculobullous disorder that is characterized by mucocutaneous erosions or blisters. The term “pemphigus” includes PV, pemphigus foliaceus, and paraneoplastic pemphigus, with PV being the most widely diagnosed form of pemphigus.

The disease is caused by pathogenic antibodies directed against desmoglein (Dsg) 1 and 3, which are members of the desmosomal cadherin family. The *in vivo* binding of these anti-Dsg autoantibodies (mainly IgG4 and IgG1) causes a loss of adhesion between keratinocytes, and the resultant formation of intra-epidermal blisters [Amagai 1995]. These blisters eventually lead to erosions in the skin which, prior to the corticosteroid era, frequently resulted in mortality.

1.2. Current Treatments

Systemic glucocorticoids have been the cornerstone of management for PV, reducing mortality to approximately 5% to 15% [Robinson 1997; Langan 2008]. An optimal steroid-sparing agent has not yet been identified, due in part to the paucity of randomized controlled studies conducted to date.

Intravenous (IV) rituximab, a chimeric IgG1 monoclonal antibody that depletes B-cells by targeting the B-cell-specific CD20 antigen, was identified in case-series reports as a successful treatment for severe or refractory PV [Ahmed 2006; Cianchini 2007; Joly 2007; Eming 2008; Kim 2011; Kasperkiewics 2012; Leshem 2013; Lunardon 2012], and in a single case report as a first-line therapy [Craythorne 2011]. The reduction of pathogenic antibodies via targeted B-cell depletion forms the basis for the use of rituximab in the treatment of PV, and clinical response to rituximab has correlated with B-cell depletion [Mouquet 2008; Eming 2008; Colliou 2013]. Rituximab, which is not approved for use in PV, has not been evaluated for the treatment of PV in randomized prospective clinical studies, and its use remains limited given the need for infusion suites for drug administration.

1.4. Rationale

Although no cure is currently available for PV, the efficacy of systemic corticosteroids (often administered at high doses and concomitantly with other immunosuppressive treatment) in managing PV has been well demonstrated [Harman 2003]. Systemic corticosteroids are currently the most commonly utilized therapy for the management of PV. Multiple side-effects associated with high-dose corticosteroids, however, increase morbidity and may necessitate the use of adjuvant steroid-sparing therapies.

For subjects failing PV treatment due to adverse events (AEs) associated with high-dose steroid treatment or other immunosuppressants, or due to dosing inconvenience (as in the case of rituximab with the attendant need for an infusion suites), additional therapeutic approaches are needed to appropriately treat PV.

The objective of this study is to evaluate the efficacy, tolerability, and safety of ofatumumab injection for SC use (ofatumumab SC) at a dose of 20 mg administered every 4 weeks (with an additional 20 mg loading dose [ie, 40 mg total] at both Week 0 and Week 4) in subjects with PV. It is anticipated that with sustained B-cell depletion in the presence of ofatumumab SC, and the resultant reduction of pathogenic anti-Dsg autoantibodies in PV, that clinical remission of the disease will result.

Subjects completing the study and meeting all entry criteria will be offered the option to participate in an extension study (OPV117059), which will start after completion of the Week 60 visit. That is a separate study which will not be considered in this SAP. Whatever the data collected for study (OPV117059) will be handled separately.

1.5. Investigational Product

Initially, syringes containing 0.6 mL (60 mg) of concentration 100 mg/mL drug product was provided. For study centers initiated using the dilution method for study treatment preparation, an unblinded pharmacist (or appropriately-qualified designee) at the study center will prepare each dose via a dilution process according to detailed instructions. The 60 mg ofatumumab syringes was diluted using placebo syringes to achieve the 20 mg ofatumumab (concentration 50 mg/mL) dose.

When available, GSK supplied ofatumumab SC in prefilled glass syringes containing 0.4 mL (20 mg) of concentration 50 mg/mL drug product and matching placebo prefilled glass syringes containing 0.4 mL of normal saline.

2. STUDY OBJECTIVE(S) AND ENDPOINT(S)

2.1. Study Objective(s)

2.1.1. Primary Objective

The primary objective of the study is to determine the efficacy, based on disease remission, of ofatumumab SC at a dose of 20 mg administered every 4 weeks (with an additional 20 mg loading dose [ie, 40 mg total] at both Week 0 and Week 4) in subjects with PV.

2.1.2. Secondary Objectives – Efficacy and Pharmacodynamic

The secondary efficacy and pharmacodynamic (PD) objectives of the study include:

- To evaluate disease flare/relapse during treatment with ofatumumab SC.
- To evaluate reductions in steroid dose while maintaining disease control.
- To determine the extent of B-cell depletion and repletion following ofatumumab SC.

2.1.3. Secondary Objectives – Pharmacokinetic

The secondary pharmacokinetic (PK) objective of the study is to assess the population pharmacokinetics of ofatumumab SC.

2.1.4. Secondary Objectives - Safety

- To evaluate the immunogenicity of ofatumumab SC.
- To evaluate the safety and tolerability of ofatumumab SC.

2.2. Study Endpoint(s)

In the discussion of study endpoints, please note the following:

- *Minimal steroid therapy* is defined as an oral prednisone/prednisolone dose of ≤ 10 mg/day.
- *Remission* is defined as the absence of new or nonhealing (established) lesions for ≥ 8 weeks (Note: Subjects with existing, healing lesions and no new lesions for ≥ 8 weeks may be considered in remission.).
- *Remission on minimal steroid therapy* is defined as the absence of new or nonhealing (established) lesions while on an oral prednisone/prednisolone dose of ≤ 10 mg/day for ≥ 8 weeks.
- *Sustained remission (SR)* is defined as the absence of new or nonhealing (established) lesions for ≥ 8 weeks that is sustained until Week 60.
- *Flare/relapse* is defined as the appearance of ≥ 3 new lesions within 1 month that do not heal spontaneously within 1 week, or when there is an extension of lesions that were present at the randomization visit.
- *Disease Control* is defined as no new lesions for ≥ 2 weeks [Murrell 2008]

2.2.1. Co-Primary Efficacy Endpoints

Some of the analysis bullet points described in the original protocol is removed as requested by Novartis (section 2.2.2 - 2.2.6).

Two co-primary efficacy endpoints will be evaluated:

- Time to SR on minimal steroid therapy (defined as time from randomization to the time the subject initially tapered his/her oral prednisone/prednisolone dose to ≤ 10 mg/day and maintained ≤ 10 mg/day of oral prednisone/prednisolone with no new or nonhealing (established) lesions for ≥ 8 weeks AND maintained that status until Week 60).
- Duration of remission on minimal steroid therapy (defined as total time [sum] of all periods of remission while on minimal steroid therapy [oral prednisone/prednisolone dose of ≤ 10 mg/day] up to Week 60).

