6.2.2. Secondary Efficacy Endpoints

- Proportion of subjects achieving remission on minimal steroid therapy (defined as subjects who had an absence of new or nonhealing lesions while on an oral prednisone/prednisolone dose of ≤ 10 mg/day for ≥ 8 weeks) at Week 60.
- Time to remission while on minimal steroid therapy (defined as time from randomization to the time the subject initially tapered his/her oral prednisone/prednisolone dose to ≤ 10 mg/day and maintained ≤ 10 mg/day of oral prednisone/prednisolone with no new or nonhealing lesions for ≥ 8 weeks) by Week 60.
- Time to initial flare/relapse (defined as the time from randomization to the time that ≥ 3 new lesions within 1 month appear and do not heal spontaneously within 1 week, or to the time when there is an extension of lesions that were present at the randomization visit) by Week 60.
- Proportion of subjects who did not flare/relapse (defined as subjects who achieved remission on minimal steroid therapy and did not subsequently have a flare of disease) by Week 60. A flare/relapse is defined as new lesions that do not heal spontaneously within 1 week, or when there is an extension of lesions that were present at the randomization visit.
- Time to remission off steroid therapy by Week 60 (defined as the time from randomization to the time the subject initially tapered off all steroids for ≥ 8 weeks with an absence of new or nonhealing lesions).
- Proportion of subjects achieving remission while off steroid therapy by Week 60.
- Number of days a subject maintained minimal steroid therapy (an oral prednisone/prednisolone dose of ≤ 10 mg/day in the absence of new or nonhealing lesions) by Week 60.
- Cumulative dose of corticosteroids.

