2.2.2. Secondary Efficacy Endpoints

- Proportion of subjects achieving remission on minimal steroid therapy (defined as subjects who had an absence of new or nonhealing lesions while on an oral prednisone/prednisolone dose of ≤ 10 mg/day for ≥ 8 weeks) at Week 60 (i.e. proportion of subjects achieving sustained remission).
- Time to remission while on minimal steroid therapy (defined as time from randomization to the time the subject initially tapered his/her oral prednisone/prednisolone dose to ≤ 10 mg/day and maintained ≤ 10 mg/day of oral prednisone/prednisolone with no new or nonhealing lesions for ≥ 8 weeks) by Week 60.

- Time to initial flare/relapse (defined as the time from randomization to the time that ≥ 3 new lesions appear within 1 month and do not heal spontaneously within 1 week, or to the time when there is an extension of lesions that were present at the randomization visit) by Week 60. For analysis purposes, “1 month” is assumed to be 30 days and “1 week” is assumed to be 7 days.
- Proportion of subjects who did not flare/relapse (defined as subjects who achieved remission on minimal steroid therapy and did not subsequently have a flare of disease) by Week 60.
- Cumulative dose of corticosteroids.

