- Once the dose is reduced to 10 mg, an attempt at reducing the steroid dose further need only be attempted until the first flare/relapse occurs. In the event of a flare/relapse at a prednisone/prednisolone dose of ≤10 mg/day, the dose will be temporarily increased in order to reestablish disease control (no new lesions for >2 weeks); after disease control is maintained, further steroid tapering attempts to <10 mg will be at the investigator's discretion.

A steroid administration log capturing the tapering of the medication will be collected in the eCRF.

A by-visit summary of oral prednisone/prednisolone dose and a summary of each subject's cumulative oral prednisone/prednisolone dose will be presented using descriptive statistics for each treatment group. Additionally, since a subject's steroid dose at each visit is dependent upon his/her stable dose achieved during Screening, descriptive statistics will be presented for the oral prednisone/prednisolone dose at each visit for each stable dose level of oral prednisone/prednisolone achieved during Screening for each treatment group.

Tables summarizing oral prednisone/prednisolone dose will be presented for the ITT population.

The information collected in the steroid taper log will be presented in a data listing for the ITT population.

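### The SAP drops three of eight secondary efficacy endpoints, including both off-steroid remission endpoints, without naming, dating or individually justifying the removals, which creates a risk of selective reporting

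*SAP*

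**What the plan says.** Protocol 6.2.2 includes, as its fifth to seventh secondary efficacy endpoints, "Time to remission off steroid therapy by Week 60", "Proportion of subjects achieving remission while off steroid therapy by Week 60" and "Number of days a subject maintained minimal steroid therapy". None appears in SAP 2.2.2, whose five entries end with "Cumulative dose of corticosteroids".

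The explanation in SAP 2.2.1 is one sentence: "Some of the analysis bullet points described in the original protocol is removed as requested by Novartis (section 2.2.2 - 2.2.6". It does not say which items went, when, or why.

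SAP Section 1 gives a general reason: the study stopped early with 69 patients, so the analyses were cut back. The cuts it specifies are the subgroup analyses and the multiplicity procedure. It also states: "All the core analyses were kept as per the original protocol analysis plan". The SAP modification history itemises only pharmacokinetic, pharmacodynamic and pharmacogenetic changes.

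On timing, the rationale for Amendment 7 (25 April 2016) in Protocol Appendix 15 begins "Given the study had been terminated, the Sponsor unblinded" and says this was to help investigators go on monitoring their subjects. The SAP final draft is dated 7 April 2017 and the effective version 29 March 2018. SAP 3.1, 6.3 and 10.2 nonetheless describe unblinding as still to come.

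**The concern.** When a sponsor shortens a pre-specified endpoint list late in a study, a reader needs to know what was removed, why, and whether anyone who decided could have known the treatment arms. Here the first has to be worked out by comparing two lists, the second is answered only in general terms, and the third cannot be answered.

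If the choice was made with knowledge of the arms, the retained endpoints could give a more favourable or more coherent picture than the full set. If it was not, the sponsor has left itself unable to show that. The substance also matters. Protocol Table 3-1 places both off-steroid endpoints under the primary objective, and they are the only listed efficacy endpoints that require a steroid dose of zero.

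**Working it through.** **Step 1. Compare the lists.** Ranks follow Protocol 6.2.2, which Protocol 8.3.3.2 also makes the testing order. Objectives come from Protocol Table 3-1.

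| Rank | Endpoint (short form) | Objective served | SAP 2.2.2 |
|---|---|---|---|
| 1 | Proportion in remission at ≤10 mg/day, Week 60 | Primary | Kept |
| 2 | Time to remission at ≤10 mg/day | Primary | Kept |
| 3 | Time to first flare | Flare | Kept |
| 4 | Proportion flare-free after remission | Flare | Kept |
| 5 | Time to off-steroid remission | Primary | Dropped |
| 6 | Proportion in off-steroid remission | Primary | Dropped |
| 7 | Lesion-free days at ≤10 mg/day | Steroid reduction | Dropped |
| 8 | Cumulative steroid dose | Steroid reduction | Kept |

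- Dropped overall: 8 − 5 = 3, and 3/8 = 37.5%.
- Off-steroid endpoints: 2 planned, 0 kept.
- Secondary endpoints supporting the primary objective: 4 planned, 2 kept.
- Steroid-reduction objective: 2 planned, 1 kept. The one kept, cumulative dose, carries no condition on lesions, whereas the SAP still words the objective as reducing dose while disease stays controlled.

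The SAP cites Amendment 6 as its base. The logs for Amendments 6, 7 and 8 record no removal of a secondary efficacy endpoint, so the protocol version does not explain the difference.

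**Step 2. Order the dates.**

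- Unblinding is recorded in Amendment 7, 25 April 2016.
- The change of sponsor to Novartis, which made the request, is recorded in Amendment 8, 5 September 2016.
- The SAP final draft is dated 7 April 2017: 365 − 18 = 347 days after Amendment 7, about 11 months.
- The effective SAP is dated 29 March 2018: 730 − 27 = 703 days after Amendment 7, about 23 months.

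Two things stop this from settling the sequence. SAP 3.1, 6.3 and 10.2 place unblinding in the future. The log also gives 35 randomised at both Amendment 7 and Amendment 8, while the SAP gives 69.

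**Step 3. Ask whether small numbers explain the choice.** Reproduce the design first. The hazard ratio is ln(0.46)/ln(0.20) = 0.48248, as in Protocol 8.2.1. The required events by Schoenfeld's formula are 4(1.960 + 1.282)²/(ln 0.48248)² = 79.1, rounded up to 80, which matches the protocol.

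Now take 69 patients with the design's 13% loss and average sustained-remission rate of (0.54 + 0.80)/2 = 0.67:

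- expected events = 69 × 0.87 × 0.67 = 40.2;
- power for time to sustained remission = Φ(√(40.2/4) × 0.7288 − 1.960) = Φ(0.351) ≈ 64%, against 90% at 80 events.

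This assumes that all 69 could be followed to Week 60; truncated follow-up would lower it. Loss of precision is therefore real, but it applies to the retained time-to-event and proportion endpoints as well. It justifies a simpler plan without identifying these three endpoints as the ones to cut.

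**Step 4. Check what still measures steroid use.** Both co-primaries and secondary endpoints 1 and 2 require ≤10 mg/day. Cumulative dose stays, and SAP 10.6 adds "A by-visit summary of oral prednisone/prednisolone dose". Reduction is covered. Remission at zero dose has no visible planned analysis.

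**The case against.** The strongest reply is that the cut follows the protocol's own ranking. Ranks 1 to 4 survive intact, and SAP Section 11 lists the same four and refers to them as key secondary endpoints. Ranks 5 to 7 go, and rank 8 matches the dose summary already planned in SAP 10.6. That is a plausible reason unrelated to results. It stands as a possibility, but the SAP never states it, and a cut by rank alone would not keep rank 8.

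A second reply is that off-steroid events would be rarer. On the taper table, a flare-free subject starting at 60 mg reaches 10 mg at Week 18 and 0 mg at Week 26, so eight weeks at each level ends at Week 26 and Week 34. After a flare at or below 10 mg, further tapering is discretionary. Fewer events are thus likely, which supports a descriptive summary. It does not support silence, since Week 34 falls well inside the 60 weeks.

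Third, rank 7 overlaps the co-primary on duration of remission, differing mainly by that endpoint's eight-week requirement. This is fair, and its loss matters less than the other two.

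Fourth, a reader might infer that endpoints were removed with the results in view. The documents do not support that. The request is undated, the recorded unblinding was for subject monitoring, SAP Section 1 says advanced SAP versions already existed when sponsorship moved, and nothing says comparative efficacy data had been seen. The removal is also disclosed, if thinly.

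Finally, SAP 2.2.3 and the contents entries after 11.2.3 are not visible, so an off-steroid analysis placed there cannot be excluded. The 2.2.2 list itself shows no redaction.

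**Conclusion.** The point holds as one of transparency and reporting risk. Three of eight secondary efficacy endpoints were removed from the secondary list at the sponsor's request. They include both off-steroid endpoints and half of the secondary endpoints tied to the primary objective. No removed endpoint is named, dated or individually justified.

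Two stronger readings should be resisted. Selective reporting is not shown: removal after unblinding is an inference from the Amendment 7 rationale set against the SAP dates, and the SAP's own text contradicts it. Nor does the taper's goal go unmeasured: the body text of both documents gives the goal as reducing or eliminating steroids, and reduction remains well covered. What is lost from view is remission after elimination, plus one of two endpoints for steroid reduction.

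The practical consequence is moderate, because every p-value is now nominal with no multiplicity control. The conclusion assumes that the unredacted SAP 2.2.2 list is complete and that the hidden sections do not reinstate these endpoints.

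**What to change.** - Restore the three endpoints to SAP 2.2.2 with the methods in Protocol 8.3.6.5: stratified log-rank for time to off-steroid remission, stratified CMH for the proportion, and ANCOVA with treatment and strata for days on minimal steroid therapy. Report nominal p-values as for the other endpoints, or descriptive summaries alone if events are sparse. Because the protocol already fixed these methods, reinstating them adds no new analytic choice.
- In the modification history, list each efficacy endpoint still omitted, with its reason and the date of the decision relative to unblinding. If an off-steroid analysis sits in a section not visible here, say so and cross-refer to it.
- Reconcile the Amendment 7 rationale with SAP 3.1, 6.3 and 10.2 by stating who was unblinded, when, and to what. Explain the 35 and 69 randomised counts.

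The cost is about three tables. SAP 11.2.1 and 11.2.2 already draw on the steroid taper log and lesion evaluations, so no new data are needed. The drawback is low precision with 69 patients, which the report should state beside the estimates.
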